-	Study Week		Week 0	Week 1	Week 2	Week 3	Week 4	Week 5	Week 6 or ET at week 6	Week 7	Week 8	Week 9	Week 10	Week 11	Week 12	Any visit other than at week 6
Medical His	tory	X														
Physical Ex	am	Х														
MINI		Х														
Pregnancy Test (Females only)		X														
Post-Screer Pregnancy Checklist	ning		X			Х			X			Х				
ECG		Х							Х						Х	Х
Labs (CMP, Panel, CBC CRP, IL6, T	, Hs- NFα)	X							X						Х	X (only CMP, Lipid panel, and CBC)
Lab (HbA10	C) ⁴	Х														
Vital Signs		X	Х	Х	Х	Х	Х	Х	Х	Х	Х	Х	Х	Х	Х	Х
Height		X	Х													
Weight		X	Х	Х	Х	Х	Х	Х	Х	Х	Х	Х	Х	Х	Х	Х
Waist Circumferer	nce		Х						Х						Х	
TLFB ¹		Х	Х	Х	Х	Х	Х	Х	Х	Х	Х	Х	Х	Х	Х	Х

VAS	Х	Х	Х	Х	Х	Х	Х	Х	Х	Х	Х	Х	Х	Х	Х
Urine Drug Screen	Х	Х	Х	Х	Х	Х	Х	Х	Х	Х	Х	Х	Х	Х	Х
Fagerstrom Test	Х							Х						Х	
Adverse Events		Х	Х	Х	Х	Х	Х	Х	Х	Х	Х	Х	Х	Х	Х
PANSS		Х						Х						Х	
SANS		Х						Х						Х	
CDRS		Х						Х						Х	
CGI-S and CGI-I ²		Х						Х						Х	
CSSRS	Х	Х						Х						Х	Х
QOL		Х						Х						Х	
EPS Scales (BAS, SAS, AIMS)		Х						Х						Х	
Drug dispensing		Х	Х	Х		Х		Х		Х		Х			
Supportive Counseling		Х	Х	Х	Х	Х	Х	Х	Х	Х	Х	Х	Х	Х	

1- TLFB at screening will be completed for the past 30 days. All other visits the TLFB will collect information for the past week.

2- CGI-I will not be administered at baseline. Only CGI-S is administered at baseline.

- 3- EOT end of treatment
- 4- Lab (HbA1C) will only be performed at the screening visit

5- If ET falls on week 6, the visit should follow regular week 6 protocol. If ET falls on any other visit, follow ET protocol

Informed Consent Process: All subjects will sign IRB approved informed consent form (ICF) prior to starting any study related screening procedures. The written informed consent will be obtained by authorized study personnel. The authorized study staff will explain the study objectives, risks and benefits and overview of the study procedures to all subjects as part of the consent process.

Eligibility Review: An eligibility review will be conducted by the investigator at each site as per the inclusion exclusion criteria listed in section D of the protocol. All subject eligibility criteria will be reviewed by UMass designee prior to subject randomization.

Demographics and Medical/Psychiatric History: Subject's demographics, medical and psychiatric history will be collected as part of the screening process. All patient medical and psychiatric history will be reviewed by the investigator.

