Any clinically significant change noted from screening or if an ECG is considered abnormal and clinically significant, it will be reported as an AE and will be appropriately recorded in both the source documents and the eCRF.

Laboratory Procedures: Most of the lab procedures will be done at the site. All blood work will be done as fasting.

Routine lab panels done at site include: Hematology (CBC with diff), comprehensive metabolic panel (CMP) and lipid panel. These labs will be assessed at screening, week 6 and week 12. Routine lab panels will be collected for subjects who are early terminated. Additionally, an HbA1c test will be conducted at screening only. Approximately four tablespoons of blood will be taken at each blood draw.

Lab samples for Hs-CRP, IL6 and TNF -alpha will be collected by sites and stored at -80F. It will be batch shipped to UMass every 6 months. These will be analyzed at UMass Memorial labs. CRP, IL-6 and TNF- α are well established inflammatory markers that are associated with both psychopathology and metabolic side effects in patients with schizophrenia. We will analyze how brexpiprazole treatment might affect these inflammatory markers.

Hematology (CBC)	Comprehensive metabolic panel	Lipid Panel
Hematocrit	Alanine transferase	Total cholesterol
Hemoglobin	(ALT)	Chol, HDL
Platelets	Albumin	Triglyceride
	Total protein	Chol, LDL

Routine Lab Assessments at site:

Red blood cell	Alkaline	Chol, VLDL
count	phosphatase (ALK-	Cholesterol/DL ratio
Total and	P)	
differential	Aspartate	
(absolute) white	transferase (AST)	
blood cell count	Bicarbonate	
	Blood urea nitrogen	
	(BUN)	
	Creatinine	
	Glucose	
	Potassium	
	Sodium	
	Chloride	
	Estimated	
	glomerular	
	glomerular filtration	
	rate (eGFR)	

Future Testing: Blood samples will be collected at screening, week 6 and week 12 for use in future research related to schizophrenia. All samples will be labelled with a study ID. Only members of the research team will be able to derive an individual's identity from their study ID code. The key to the code is stored on secure server and can only be accessed through password-protected computer Sub-sites will store these at -80F and batch ship them to the UMass Psychotic Disorders Research Program at UMass Medical School for storage and future extraction/genotyping. The lead site will store all samples indefinitely.

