Screening Visit: Screening visit assessments includes: Fasting blood samples for lipid profile, comprehensive metabolic profile, CBC, hs-CRP, IL-6 and TNF-α will be obtained at the screening visit. Potential subjects will undergo a diagnostic evaluation. Psychiatric diagnosis will be determined using the Mini International Neuropsychiatric Interview (MINI). A medical evaluation, including weight, height, vital signs, a physical examination, and review of systems will be performed. A urine pregnancy test will be performed on all women of childbearing potential. The subjects will be given an appointment card for their next visit which will also provide a reminder for the use of appropriate birth control. In addition, a urine drug screen, and a 12-lead EKG will be performed. A 30-day timeline follow-back will be administered at screening visit to assess current substance use and Fagerstrom test will assess smoking status.

Following the screening visit and prior to baseline visit, the subject's primary care provider and/or psychiatrist will be notified of their participation in the study in order to adequately screen subjects, ensure that only eligible subjects are enrolled, and minimize subject risk.

All screening procedures will be completed and reviewed by PI for eligibility criteria prior to randomization/baseline visit.

Randomization: After completion of all screening assessments, all patient eligibility screening documents will be sent to UMass for review and eligibility confirmation. Once a patient is deemed eligible, a randomization ID and a randomization condition (brexpiprazole versus control) for the subject will be generated. The randomization condition will be accessible to the site and their pharmacy and will be used to prepare the corresponding study treatment. Once a subject has been assigned a randomization ID, they will be identified in the CRF by this randomization ID for the duration of their study participation.

Baseline Visit: Subjects will be randomly assigned to switch to brexpiprazole (brexpiprazole group) or remain on the same antipsychotic medication (control group).

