Study intervention: Brexpiprazole switch: For the brexpiprazole group, an overlap and taper switch method will be used. The current antipsychotic medication will be tapered following standard clinical practice and discontinued over a time period of 6 weeks. Brexpiprazole will be started at 1mg/day for 4 days, and 2mg/day for 3 days, and then titrate by up to 1mg/day increase every 3 days to reach 4mg/day, or as much and as fast as the participant can tolerate. Participants will stay on 4mg/day or the highest tolerable dose until the end of the study.

Medication adherence will be measured via pill counts at weekly visits. The study staff will discuss pill count data with participants to emphasize the need to take the study medication.

If participants cannot tolerate brexpiprazole after randomization, it will be stopped, though the participant may continue to be followed on another treatment (ideally their pre-study antipsychotic medication) for the remaining weeks of the study. The subject will then continue the rest of the study on their previous antipsychotic medication.

The following assessments will be completed at baseline visit:

- 1) Anthropometric measures (weight, waist circumference and height at screening to be used) and Vital signs
- 2) Weekly TLFB
- 3) Drug screen
- 4) Post-Screening Pregnancy Checklist
- 5) AE review
- 6) PANSS, SANS, QLS, CGI-S
- 7) C-SSRS, EPS scales, CDRS
- 8) Supportive counseling

Week 6 and week 12 visits: The following assessments will be done at week 6 and 12.

- 1) Anthropometric measures (weight, waist circumference) and Vital signs
- 2) Weekly TLFB
- 3) Drug screen
- 4) Post-Screening Pregnancy Checklist (Week 6 only)
- 5) AE review
- 6) PANSS, SANS, QLS, CGI-S
- 7) C-SSRS, EPS scales, CDRS
- 8) Supportive counseling
- 9) ECG
- 10)Labs (CMP, CBC, lipid panel)
- 11)Labs hs-CRP, IL-6 and TNF-alpha collected and stored at -80F
- 12)Fagerstrom test

Week 2, 3,4,5,7,8,9,10,11 visits: These visits may be completed virtually through a secured platform depending on the most current COVID situation. During the virtual routine follow up visits, vital signs and urine drug screen will be unable to be collected; but all subjects who go through the switch will have demonstrated no clinically significant changes in vitals, ECG, or lab results in prior long visits. The following assessments will be administered at these weekly visits:

- 1) Vital signs and anthropometric measures (weight)
- 2) Urine drug screen

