If the subject is terminated from the study on what would be their week 6 visit, they will complete all the assessments that are required in a regular week 6 visit. If the subject is terminated from the study at any other point, only safety procedures will be performed (listed below).

- 1. Vital signs and anthropometric measures (weight)
- 2. Urine drug screen
- 3. TLFB
- 4. AE review
- 5. Safety labs (CMP, CBC, lipid panel)
- 6. ECG
- 7. CSSRS

G. TREATMENT OF SUBJECTS

Study Drug Dose and Administration

The study drug brexpiprazole (Rexulti) will be administered orally. Subjects will be randomly assigned to either switch to brexpiprazole or remain on the same antipsychotic medication (treatment as usual). Subjects randomized to brexiprazole treatment will be titrated as per section F (study intervention). Study participants randomized to brexpiprazole treatment will be titrated to 4mg/day or the highest tolerable dose as per the study MD's clinical judgement until the end of the study. Dose de-escalation due to tolerability will be allowed in the study. If subjects recover, the dose can be increased to the 4mg or the highest tolerable dose as per the MD's clinical judgement. Patients who are unable to tolerate a minimum dose of 1 mg will be withdrawn from the study

Study Drug

Commercially available brexpiprazole will be provided directly to all sites by Otsuka Pharmaceuticals. Study drug will be provided as 1mg and 2mg tablets. Subjects will take medications as dispensed by their site's Investigational drug pharmacy.

Storage and Drug Accountability

The study drug will be stored as per the drug insert. The sites are required to maintain current drug dispensation and accountability logs throughout the study. All unused supplies will be checked against the drug movement records during the study and/or at the end of the study.

Prohibited Medications

Currently on the following antipsychotics

- Aripiprazole
- Cariprazine

Currently on medications to treat substance use such as:

- Disulfiram,
- Naltrexone,
- Acamprosate,
- Methadone,
- Buprenorphine,
- Varenicline
- Bupropion

Special Consideration for Concomitant Medications with Brexpiprazole

Medications	Intervention
-------------	--------------

Strong CYP3A4 inhibitors	With concomitant use of brexpiprazole with a
	strong CYP3A4 inhibitor, reduce the brexpiprazole
Examples: itraconazole,	dosage and administration [see drug insert
clarithromycin, ketoconazole	dosage and administration (2.5)]

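### Early-termination blood draws leave out hs-CRP, IL-6 and TNF-alpha, so subjects who leave before week 6 add no post-baseline value to the planned marker analysis

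*Combined protocol and SAP*

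**What the plan says.** Section E, Laboratory Procedures, states the aim: "We will analyze how brexpiprazole treatment might affect these inflammatory markers". The pre-treatment sample is taken at screening (Section F: "Fasting blood samples for lipid profile, comprehensive metabolic profile, CBC, hs-CRP, IL-6 and TNF-α will be obtained at the screening visit"). The week 6 and week 12 lists in Section F both include "Labs hs-CRP, IL-6 and TNF-alpha collected and stored at -80F", and Table 1 agrees.

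For early termination, the laboratory row of Table 1 is restricted to "only CMP, Lipid panel, and CBC". Item 5 of the Early Termination Visit list in Section F names the same panels: "Safety labs (CMP, CBC, lipid panel". The one exception, in Table 1 footnote 5 and in Section F, is termination at the week 6 visit, when the full week 6 assessments are done, markers included.

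On handling, Section E says of the frozen marker samples "It will be batch shipped to UMass every 6 months", and then "These will be analyzed at UMass Memorial labs". It does not say when assays are run or whether one subject's samples share a run. Section L gives no model for the markers.

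**The concern.** The protocol promises a treatment comparison on three markers and then, by rule, does not collect them at a visit where blood is already being drawn. Subjects who leave early are the ones for whom no other post-baseline value may exist. The loss reduces precision. It could also distort the comparison if leaving differs between arms and is related to the markers.

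That link is plausible on the protocol's own account. Section E describes the markers as associated with psychopathology and metabolic side effects, and Section F withdraws subjects for psychiatric worsening or for repeated exclusionary laboratory values. Section G also has a withdrawal rule for intolerance of the study drug, which can apply only to the switch arm. Section F allows such subjects to stay in follow-up, so these two passages need to be reconciled.

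The shipping rule raises a second, weaker question: whether a subject's before and after samples might be measured in different assay runs.

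**Working it through.** **Inputs from the protocol.** 50 randomized, 20% discontinuation, 40 completers (Section D). Marker draws at screening, week 6 and week 12 (Table 1, Section F). Shipments every 6 months, about 26.09 weeks (Section E). Expected enrolment 15 February 2018 to 20 November 2023 (Synopsis).

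**Assumed, because not stated.** 1:1 allocation; timing of dropout; a screening-to-baseline gap *s* of 0 to 4 weeks; enrolment uniform against the shipping calendar; a ratio *r* of between-run SD to the SD of change.

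**1. The plan's own figure.** 40 / (1 − 0.20) = 50, which reproduces. Expected leavers: 0.20 × 50 = 10.

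**2. Who has a marker value under the present rule.**
- Leaves before week 6: screening only.
- Terminates at the week 6 visit: screening and week 6.
- Leaves after week 6 but before week 12: screening and week 6, nothing later.
- Completes: all three.

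**3. Loss of precision for a contrast using any post-baseline value.** With *f* the share of the 10 leavers who go before week 6, the number with a value is 50 − 10*f*. With even losses by arm, the SE ratio against all 50 is √(50 / (50 − 10*f*)).
- *f* = 0.25: 47.5 subjects, √(50/47.5) = 1.026
- *f* = 0.5: 45 subjects, √(50/45) = 1.054
- *f* = 1: 40 subjects, √(50/40) = 1.118

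Uneven losses cost slightly more. If all 10 leave before week 6, split 8 and 2, the ratio is √[(1/17 + 1/23) / (2/25)] = √(0.1023/0.08) = 1.131.

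**4. Bias, as a scenario only.** If leavers differ from stayers by *D* SD, a contrast that drops them is off by the difference in leaving proportions times *D*. An assumed split of 8 of 25 against 2 of 25 gives (0.32 − 0.08) × *D* = 0.24*D*, or 0.12 to 0.24 SD for an assumed *D* of 0.5 to 1. With equal leaving and equal *D* in both arms it is zero.

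**5. Shipping.** The chance that a shipping date falls between the screening and week 12 samples is (12 + *s*) / 26.09: 0.460 for *s* = 0, 0.537 for *s* = 2, 0.613 for *s* = 4. Enrolment spans 69.1 months, or 11.5 six-month periods, so about 50/11.5 = 4.3 subjects per shipment.

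If, and only if, each shipment is its own assay run, the SE ratio for a change score is √(1 + 2*pr*²), with *p* the share split.
- *r* = 0.25: √(1 + 2 × 0.460 × 0.0625) = 1.028 to √(1 + 2 × 0.613 × 0.0625) = 1.038
- *r* = 0.5: √(1 + 2 × 0.460 × 0.25) = 1.109 to √(1 + 2 × 0.613 × 0.25) = 1.143

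A simulation with 40 completers, 20 per arm, gave SE ratios of 1.11 to 1.14 at *r* = 0.5 and a mean between-arm shift of about zero.

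**The case against.** The markers are not among the primary, secondary or additional objectives in Section C, and this is a 50-subject feasibility study. Section F deliberately confines early-termination visits outside week 6 to safety procedures; PANSS, SANS and QOL, which serve secondary objectives, are left out there too. Subjects who withdraw consent give no further data (Section H), so an added tube would not reach every leaver. All of this stands, and it keeps the point small. It does not remove the mismatch between a stated analysis and a collection rule that can be changed at almost no cost.

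A reader might infer that the whole marker analysis is completer-only. The documents do not support that. Anyone who reaches or terminates at week 6 has a post-baseline value, subjects who stop brexpiprazole may remain in follow-up, and a repeated-measures model could use week 6 values. Only the week 12 value is confined to those who stay to the end.

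A reader might also infer that six-monthly shipping makes the estimates noisier. The protocol fixes a shipping interval and a place of assay, not a run schedule. Frozen samples could be held and run together. Even if they were not, randomized arms would share the runs, so the cost would be precision and not expected bias.

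**Conclusion.** The point holds as a minor design gap. The early-termination rule discards marker information that the protocol says it wants, affecting at most 10 of 50 subjects at the planned discontinuation rate. The SE cost is about 3% to 12% as the share of leavers going before week 6 runs from a quarter to all of them, with even losses by arm. The upper figure is an extreme case, and it overstates what can be recovered, because some leavers will withdraw consent.

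Bias is possible but cannot be sized from the documents. They give an overall discontinuation rate only, and the 0.12 to 0.24 SD scenario rests wholly on an assumed split between arms and an assumed difference between leavers and stayers.

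The shipping point is secondary and conditional. The 46–61% split of sample pairs follows from the stated interval and an assumed gap of 0 to 4 weeks. The SE increase of about 3–4% or 11–14% needs both assay on arrival and an assumed run SD of 0.25 or 0.5 of the SD of change. What is missing is a statement about assay runs.

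**What to change.** 1. In the early-termination column of Table 1 and in item 5 of the Early Termination Visit list, add hs-CRP, IL-6 and TNF-alpha for subjects who attend that visit.
2. In Section L, name the marker analysis: a repeated-measures model adjusted for the screening value, with the early-termination value entered at its actual study week.
3. In Section E, Laboratory Procedures, add one sentence: all samples from a subject are assayed in the same run. The six-monthly shipping rule can stay.

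Cost: a short wording change and at most about 10 extra tubes at a draw already scheduled. Subjects who withdraw consent will contribute none. An early-termination value reflects the time of leaving, so it only partly replaces the week 12 value. The assay-run sentence may mean that the laboratory holds some samples until a subject's set is complete.

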"No desire at all" (marked with a "0") and on the left side with "Worst imaginable desire" (marked with a "100" with a line connecting the two ends. Subjects will mark the appropriate point to indicate where their "desire for substance" falls on this line.

Fagerstrom Test: The Fagerstrom Test for Nicotine Dependence will be used to assess smoking status. Data on subjects will be collected using the Fagerstrom test as per the schedule of events.

Positive and Negative Syndrome Scale (PANSS): PANSS is a measure used to assess symptom severity in patients with schizophrenia. It consists of three sections: Positive scale has 7 items, Negative scale has 7 items and General

Psychopathology has 16 items. Each item (symptom) will be scored on a 7-point scale with higher scores representing increasing levels of psychopathology: 1) Absent, 2) Minimal, 3) Mild, 4) Moderate, 5) Moderate severe, 6) Severe, and 7) Extreme. The PANSS will be administered by a designated study staff at time points specified in the schedule of events.

Schedule of Assessment of Negative Symptoms (SANS): SANS is a 24-item scale used to assess negative symptoms based on observation and a structured interview in patients with schizophrenia. Designated study staff will administer the SANS at baseline, week 6 and week 12.

Calgary Depression Rating Scale (CDRS): The Calgary Depression Rating Scale is used to depression symptoms in subjects. The PI or a designated staff will administer the CDRS at baseline, week 6 and week 12.

Clinical Global Impression – Severity and Clinical Global Impressions – Improvement Scales (CGI-S and CGI-I): The CGI-S and CGI-I are observer rated scales. The CGI-S measures illness severity on a 7-point Likert scale 1) Normal, not at all ill, 2) Borderline mentally ill, 3) Mildly ill, 4) Moderately ill, 5) Markedly ill, 6) Severely ill, and 7) Among the most extremely ill patient. The CGI-I is used to measure improvement in illness and also uses a 7 point Likert scale: 1) Very much improved, 2) Much improved, 3) Minimally improved, 4) No change 5) Minimally worse, 6) Much worse, 7) Very much worse. The PI or a designated study staff will administer this at time points as per the schedule of events.

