Heinrichs Carpenter Quality of Life Scale (QOL): The QOL is a 21-item scale providing information on symptoms and functioning in patients with schizophrenia. A trained designated study staff will administer the QLS at baseline, week 6 and week 12.

Safety Assessments

Extra Pyramidal Symptoms (EPS) Scales: The PI or a designee will complete the following EPS scales – The Abnormal Movement Scale (AIMS), Barnes Akathasia Scale (BAS) and the Simpson Angus Scale (SAS). These movement scales will be assessed at baseline, week 6 and week 12.

Columbia Suicide Severity Rating Scale (CSSRS): The PI or a designee will administer the C-SSRS. The C-SSRS will be administered at screening,

baseline, week 6 and week 12. The C-SSRS should be administered by a clinician trained to assess and manage suicidal ideation and behavior.

Adverse Events (AE): Adverse events will be monitored at each weekly visit. The PI or the sub-investigator will review adverse events at every study visit. AE information is collected and recorded starting on the day the consent is signed until the end of an individual's participation in the study.

F. STUDY VISIT PROCEDURES AND SCHEDULE

The proposed study is a 4-site, 12-week, novel, feasibility, "proof of concept" investigation of patients who have co-occurring diagnoses of schizophrenia and current substance use disorder (alcohol, cocaine, heroin, or cannabis). Fifty patients not treated with aripiprazole or cariprazine at the time of consent will be randomly assigned to switch to brexpiprazole (the brexpiprazole group) or remain on the same antipsychotic treatment (the control group).

Informed consent will be obtained prior to the screening visit and any study procedures.

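### Sites can know the arm before the baseline symptom ratings are done, and baseline symptoms are model covariates

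*Combined protocol and SAP*

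**What the plan says.** Section F, Randomization, has the screening documents sent to the lead site, and then: "Once a patient is deemed eligible, a randomization ID and a randomization condition (brexpiprazole versus control) for the subject will be generated". The next sentence is: "The randomization condition will be accessible to the site and their pharmacy and will be used to prepare the corresponding study treatment".

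Two neighbouring statements time the assignment differently. The Screening Visit text says "All screening procedures will be completed and reviewed by PI for eligibility criteria prior to randomization/baseline visit", which treats randomization and the baseline visit as one point. The Baseline Visit paragraph likewise opens with the random assignment, although the Randomization paragraph has the treatment prepared from an arm already generated.

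The baseline ratings are introduced only by "The following assessments will be completed at baseline visit". The list that follows gives no order relative to assignment or disclosure.

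On who rates, Section E says "The PANSS will be administered by a designated study staff at time points specified in the schedule of events", "Designated study staff will administer the SANS at baseline, week 6 and week 12" and, for quality of life, "A trained designated study staff will administer the QLS at baseline, week 6 and week 12". CDRS and CGI are rated by the PI or designated staff. No masked or independent rater is described.

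Table 1 marks PANSS, SANS, CDRS, CGI-S and QOL at Visit 1, week 6 and week 12, with none at screening. TLFB and VAS are marked at screening and at every visit. Section L enters baseline substance use and clinical symptoms as covariates. Section F, Withdrawal of Subjects, measures a 20-point PANSS rise from the baseline total.

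**The concern.** Randomization makes a baseline covariate independent of treatment only if the covariate is measured without knowledge of the arm. If a rater knows who will switch, expectation can move the score, and the covariate can then differ between arms because of allocation. Adjusting for it can carry that difference into the treatment estimate.

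Open-label follow-up is built into a comparison of switching with staying on the same drug. An arm-aware baseline is not, because the ratings could be made before anyone who rates knows the arm.

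The outcomes exposed are the five clinician-rated secondary scales. For these, Visit 1 is the only pre-treatment value, so no screening rating can replace it. The primary outcomes, TLFB and VAS, also have screening values and are less exposed, although the plan does not say which visit supplies their baseline.

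**Working it through.** **The plan's own figure.** Section D randomizes 50 to have 40 completers at 20% discontinuation: 40 / (1 − 0.20) = 50, which reproduces. The order of rating does not change it. The allocation ratio is not stated; 1:1 is assumed, giving 20 (completers) to 25 (randomized) per arm.

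**Sequence.**
1. Required before the arm is generated: screening procedures and eligibility confirmation. No baseline rating is a condition.
2. Available to the site from then on: the arm.
3. Rated at Visit 1 by site staff: PANSS, SANS, CDRS, CGI-S, QOL.
4. Rule placing step 3 before step 2: none found.

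A site that rates first complies, and so does a site that rates after seeing the arm.

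**Effect on an adjusted difference.** Assumptions, none from the documents: no true effect, outcomes in SD units, baseline-outcome correlation ρ, and baseline rated higher by d in one arm. At a single visit with baseline as covariate:
- bias = −ρ × d; on a symptom scale this favours the arm rated higher at baseline
- SE = √[(1 − ρ²) × 2 / n per arm]

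With ρ = 0.5 and d = 0.2, the bias is 0.5 × 0.2 = 0.10 SD in size. SE = √(0.75 × 2 / 25) = 0.245 at 25 per arm and √(0.75 × 2 / 20) = 0.274 at 20. The bias is thus about 0.37 to 0.41 of a standard error. Over d = 0.1 to 0.5 and ρ = 0.3 to 0.7, it runs from 0.3 × 0.1 = 0.03 to 0.7 × 0.5 = 0.35 SD.

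A simulation of this analysis (20 per arm, assumed PANSS SD 15, ρ = 0.5, 4,000 runs per setting) gave:

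| Baseline shift (points) | −ρd | Simulated bias | Two-sided 5% test rejects |
|---|---|---|---|
| 2 | −1.0 | −1.1 | 6.3% |
| 4 | −2.0 | −1.9 | 7.6% |
| 6 | −3.0 | −3.0 | 10.8% |

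**Effect on the planned slope.** Section L describes group-by-time terms and does not say whether a group main effect is fitted. Using generalized least squares on weeks 6 and 12 with linear time, ρ = 0.5, d = 0.2 and residual within-subject correlation 0.3 to 0.6:
- With a group main effect, the slope bias is 0.
- Without one, the bias at week 12 is 0.09 to 0.11 SD, against SE 0.24 to 0.27, and the rejection rate is about 6% to 7%.

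**Effect on the withdrawal criterion.** With SD 15 and ρ = 0.5, change from baseline has SD 15 × √[2 × (1 − 0.5)] = 15. With no true mean change, the chance of a rise of at least 20 at one visit is P(Z ≥ 20/15) = 9.1%. If the baseline is rated 4 points too high it is P(Z ≥ 24/15) = 5.5%. After baseline, PANSS is scheduled only at weeks 6 and 12, so week 6 is the only scheduled rating before the final visit at which this could act.

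**The case against.** The strongest reply is that this rests on silence. No section says that ratings follow disclosure, and the wording that joins randomization to the baseline visit is compatible with rating first. That stands as a limit. A reader might infer that baseline ratings were in fact made with the arm known, or that the symptom results are biased; the documents show only that this is permitted.

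Second, the illustrative effect is small and vanishes for the slope if a group main effect is fitted. That also stands. The larger values need a 0.5 SD shift, for which the documents give no basis.

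Third, follow-up ratings are unblinded whatever is done, so a clean baseline may not reduce the net bias. If follow-up shifts by s in the same arm, the net bias at week 12 is s − ρd. With s = d = 0.2 and ρ = 0.5 it is 0.20 − 0.10 = 0.10 SD now and 0.20 SD with a clean baseline. With s = −0.2 it is −0.30 now and −0.20 with a clean baseline. This is a fair limit on the benefit, but relying on two unknown rating biases to cancel is no reason to leave the baseline unprotected.

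A reader might also extend the covariate argument to QOL. Section L names substance use and clinical symptoms, so QOL is not clearly a covariate.

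**Conclusion.** The point holds as a gap in procedure. The stated sequence lets site staff know the arm before making the only pre-treatment ratings of five secondary outcomes, and baseline clinical symptoms then enter the model as covariates. The resulting bias has unknown size and direction; 0.10 SD at week 12 is an illustration resting on the assumed shift and correlation.

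Three broader inferences are not supported. The concern does not reach TLFB and VAS with the same force, since both have screening values. The withdrawal consequence is confined mainly to week 6. And whether Section L should fit a group main effect, or which contrast it should report, is a separate question that this point does not settle.

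This is an inexpensive improvement for participants not yet randomized, not a defect that invalidates the trial.

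**What to change.** In Section F, reconcile the statements on when assignment takes place. Require the Visit 1 PANSS, SANS, CDRS, CGI-S and QOL, and the Visit 1 TLFB and VAS, to be completed before the arm is disclosed to anyone at the site other than the pharmacy. Add the date and time of completion to the paper source record; Section I makes paper the source but does not ask for a time. Eligibility, including inclusion criterion 3 on recent use, is still confirmed before the arm is generated, as Sections D and E require.

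In Section L, define the baseline covariates as these pre-disclosure values.

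No assessment or staff is added, and the planned 50 is unchanged. The costs are:
- The pharmacy must hold the allocation until the ratings are done, or drug must be prepared the same day.
- The change reaches only participants not yet randomized. Version 6.2 is dated January 2022 and enrollment was expected to begin in February 2018, so baseline procedure may differ within the trial.
- Follow-up ratings remain unblinded.
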